### **6.7.2 Deaths, Serious Adverse Events, and other Significant Adverse Events**

Serious adverse events refer to the adverse events that meet at least one of the following criteria:

- Lead to death
- Considered life threatening (putting participants in immediate risk of death)
- Necessitate inpatient hospitalization or prolongation (if already hospitalized)
- Result in congenital anomaly or birth defect
- Result in persistent or significant disability/incapacity
- Require medical or surgical intervention to prevent outcomes listed in the above definition of SAE
- Cause significant psychological, social, economic, or legal harm to participants or others

### **6.7.3 Clinical Laboratory Data**

No clinical laboratory data.

### **6.7.4 Pregnancy and pregnancy outcomes**

No pregnancies and pregnancy outcomes.

### **6.7.5 Other DSMB reported findings**

The number of weeks with high PM2.5 concentrations (weekly average PM2.5 level  $\geq 100 \mu\text{g}/\text{m}^3$ ) during the study will be summarized as overall and by study groups using descriptive statistics.

## **6.8 Missing Data**

Missingness refers to the absence of anticipated data as well as the reasons associated with data being absent. The frequency (percentage) of missingness for each study variable will be

summarized and presented overall as well as by study group, site, and demographics (or any combination of these characteristics).

For the analysis of the primary endpoint, the findings from the complete case analysis will be presented together with the findings based on imputed data.

### **SOURCE OF MISSING DATA**

Missing observations of primary endpoint of SFDs can occur if a caregiver fails to 1) complete and submit the weekly symptom survey in a week or in multiple weeks, or (2) complete all symptom questions in a weekly survey.

Missing observations of the secondary endpoint 1 of UHVs can occur if a caregiver fails to 1) complete and submit the weekly survey of healthcare visits in a week or in multiple weeks, or 2) report the counts of ED or UC visits and other medical visits for breathing problems.

Missing observations of the secondary endpoint 2 (total QOL score or TSS) can occur if a caregiver fails to complete and submit the PedsQL survey, or (2) complete all items in the PedsQL questionnaire.

Missing observations of the secondary endpoint 3 of PM2.5 can occur if (1) the PurpleAir monitor fails to function and read the air quality properly, (2) the child's family disables the PurpleAir monitor(s) intentionally or unintentionally, or (3) the participant does not return the PurpleAir monitor(s) and no WiFi hotspot data is available.

### **HANDLING MISSING DATA**

[figure not shown]
The patterns of missing will be inspected to determine if the missing data are missing completely at random (MCAR), missing at random (MAR), or missing not at random (MNAR). Under the scenario of MCAR, the analysis will be performed using complete data or mean imputation.

When MAR is assumed, a multiple imputation method will be used to impute missing data based on the relationships between the missing data and other observed variables. If the missing data are MNAR, then pattern mixture models will be used in imputation and inference (Little & Wang, 1996).

#### **Primary endpoint of SFDs:**

The complete case analysis may underestimate the total SFDs since all missing values will not be considered as SFDs. We will use both simple imputation and multiple imputation at the weekly level for missing values of SFDs and compare the results with a complete case analysis (Figure 3).

**Figure 3. Flow chart of handling missing data for primary endpoint SFDs.**

\*The missing data at the daily level is defined as 1) all four symptoms are missing; or 2) answering 'No' for  $\leq 3$  symptoms and the other symptoms are missing.

#### Step 1: Simple imputation at the daily level

If the caregiver reports the child has symptoms in the week but fails to report symptoms (or no symptoms) for at least one day in seven days of the week, then we will compute the frequency of symptom-free days using the remaining observed days of the week and calculate the probability of symptom-free to impute the binary outcome of the symptom (or symptom-free) for the day with the missing observation.

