## **6.6. Efficacy Analysis**

### **6.6.1. Primary Efficacy Analysis**

For the primary efficacy measure, we will test the following null hypothesis:

Null hypothesis: Mean of SFDs in the HEPA filtration home intervention group will not differ from the mean of SFDs in the control group.

vs

[figure not shown]
Alternative hypothesis: Mean of SFDs in the HEPA filtration home intervention group is larger than the mean of SFDs in the control group.

The primary endpoint is the number of caregiver-reported symptom-free days (SFD) over 24 weeks following activation of filtration (SFD is defined as a 24-hour period without coughing, wheezing, or trouble breathing). The SFD is observed through a survey each week. The survey is completed on each Sunday, and the symptom-free days are recorded from Sunday in the last week to Saturday, or the day before the survey date. The total SFDs range from 0 to 168 days (7\*24 weeks) assuming no missing data. Complete case analysis is considered as the primary analysis. For situations of missing surveys, see Handling Missing Data section 6.8.

Figure 2 shows the flowchart of surveys of symptom-free days. If a caregiver replies a "No" to the question "During the last full week (Sunday through Saturday), did your child have any coughing, wheezing, or trouble breathing?", then the recorded SFDs in this week are seven. On the other hand, if the caregiver reports a "Yes" in the previous question, and answers a "Yes" in any of the following categories "Daytime Cough", "Daytime Wheeze", "Daytime Trouble

Breathing", and "Nighttime Awakening due to Cough" for all seven days in a week, then the SFD of the survey week will be zero.

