#### Step 2 option 1: Simple imputation at the weekly level

If the caregiver fails to submit the weekly survey (i.e., During the last full week, did your child have any coughing, wheezing, or trouble breathing?) or fails to report any symptom information for seven days of the week, simple imputation will be conducted at the weekly level. The SFDs of the missing weeks will be imputed based on the average SFDs of the observed weeks.

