#### Step 2 option 2: Multiple imputation at the weekly level

The simple imputation based on weekly mean SFDs may result in biased estimates if the data are missing for more than 10% of the participants or have a large proportion of missing weeks (Eekhout et al., 2014). After evaluation of the missing proportion and pattern, multiple imputations could be used. If the caregiver fails to submit the weekly survey or no information was provided for seven days of the week, the SFDs of the week will be coded as missing. The multiple imputation will be conducted at a weekly level. The number of missing observations ranges from 0 to 24 weeks. Multiple imputation will be used to predict how many SFDs per week by the selected observed weeks based on 1) the correlations between the missing weeks and other observed weeks; and 2) the duration of the bronchiolitis symptoms (number of weeks to be included). Multivariate Imputation by Chained Equations (MICE) R package (van Buuren & Groothuis-Oudshoorn, 2011) or MI procedure in SAS software (SAS Institute Inc., 2015) will be used. The imputation process will be repeated for at least 10 times at the weekly level (Stuart et al., 2009), after which the total SFDs across 24 weeks will be calculated by adding up the observed and imputed weekly SFDs for every imputed data set. Each of the imputed data sets will be analyzed using a mixed effect model, and the parameter estimates will be combined from all analyzed data sets at the pooling phase.

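### Where daily symptom items are only partly answered, SAP Step 1 fills missing days from a set depleted of symptom-free days, so imputed mean SFDs are biased low if blanks are unrelated to the answers

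*SAP*

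**What the plan says.** SAP section 6.6.1 scores a week as seven SFDs if the caregiver answers 'No' to the weekly question. In a 'Yes' week, four items are asked for each day, and a day is symptomatic if the caregiver "answers a 'Yes' in any of the following categories". Complete case is named as the primary analysis. Section 6.8 presents imputed results beside it, and protocol section 9.4.2 plans imputation of the primary endpoint in the ITT population.

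Section 6.8 foresees item non-response: one listed source of missing SFDs is failure to "complete all symptom questions in a weekly survey". The Figure 3 footnote then defines a missing day. It begins "The missing data at the daily level is defined as 1) all four symptoms are missing" and adds a second condition: 'No' for at most three "symptoms and the other symptoms are missing".

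Step 1 is triggered as follows: "If the caregiver reports the child has symptoms in the week but fails to report symptoms (or no symptoms) for at least one day" of the seven. The instruction is "we will compute the frequency of symptom-free days using the remaining observed days of the week", and to impute the day from the resulting probability.

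Step 2 handles weeks without usable data. Under option 1, if the caregiver does not submit the survey or "fails to report any symptom information for seven days of the week, simple imputation will be conducted at the weekly level", using the average of the observed weeks. Under option 2, if the survey is not submitted or "no information was provided for seven days of the week, the SFDs of the week will be coded as missing" and multiply imputed at the weekly level.

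**The concern.** The definition of a missing day depends on the answers. A symptom-free day counts as observed only if all four items are answered; a symptomatic day needs a single recorded 'Yes'. With partial answering, the observed days of a week over-represent symptomatic days, and Step 1 carries that share into the missing days. It also sets aside the 'No' answers already recorded for the day being filled.

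Step 2 option 1 has a separate fault in the other direction. A 'Yes' week with no daily entries has no observed days for Step 1 to use, so it passes to Step 2. There it is filled from all observed weeks, including 'No' weeks scored 7, although the caregiver has said that the child had symptoms.

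At stake are the imputed mean SFDs for each arm, which are meant to show how far missing data affect the primary result. The SAP acknowledges downward bias for complete case and possible bias for weekly mean imputation, but says nothing of the kind about Step 1.

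**Working it through.** **The plan's own figures.** 168 − 70 = 98 SFDs and 20/43 = 0.465. With 98 per arm and two-sided alpha 0.05, power is 90.2% (normal) or 90.0% (t), so the stated 90% reproduces. The standard error of the arm difference is 43 × √(2/98) = 6.1 days. The documents give no rate of blank items, so everything below is conditional on an assumed rate m.

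**Probability that a day is missing.** Suppose each item is blank with probability m, independently of the other items and of the answer. For a symptom-free day, P(missing) = 1 − (1 − m)^4. For a symptomatic day with k 'Yes' items, P(missing) = m^k, because every 'Yes' item must be blank.

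| m | symptom-free | symptomatic, k = 1 | symptomatic, k = 2 |
|---|---|---|---|
| 2% | 7.8% | 2% | 0.04% |
| 5% | 18.5% | 5% | 0.25% |
| 10% | 34.4% | 10% | 1% |

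**Effect on the donor days.** Take m = 10%, k = 1 and a true symptom-free share of 50%. Among observed days the share is 0.5 × 0.9^4 / (0.5 × 0.9^4 + 0.5 × 0.9) = 0.328/0.778 = 42%. Among missing days the true share is 0.5 × 0.344 / (0.5 × 0.344 + 0.5 × 0.1) = 0.172/0.222 = 77%. Step 1 fills at about 42% where 77% is right.

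**Effect on 24-week means.** Simulation with 20,000 children per setting and 168 days. Assumptions: a two-state Markov symptom process with mean 70 (control-like) or 50 (intervention-like) symptomatic days; mean episode length 10 or 5 days; 1, 2, 3 or 4 'Yes' items on a symptomatic day with probabilities 0.50, 0.30, 0.15 and 0.05. Step 1 is applied at its expected value, and Step 2 option 1 is used for weeks with no observed day. Ranges run from episode length 10 to 5.

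| m | bias, control-like arm | bias, intervention-like arm | shift in arm difference |
|---|---|---|---|
| 2% | −1.1 to −1.8 | −0.8 to −1.4 | +0.3 to +0.4 |
| 5% | −2.7 to −4.5 | −2.0 to −3.5 | +0.7 to +1.0 |
| 10% | −5.6 to −9.2 | −4.2 to −7.1 | +1.4 to +2.1 |

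With whole-day blanks only (5% or 10% of days, unrelated to symptoms), the bias is zero to within simulation error.

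Other symptom models widen the ranges. With child-level variation set to SD 43, arm means are low by 0.7-1.5, 1.8-3.8 and 3.7-7.6 days, and the arm difference shifts by 0.3-0.4, 0.6-0.9 and 1.2-1.8. With days independent within 'Yes' weeks, means are low by 1.5, 3.7 and 7.2 days, but the difference shifts by less than 0.1 day.

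**'Yes' weeks with no daily entries.** The overall weekly mean is 98/24 = 4.08 SFDs. If a share s of weeks is 'No' and scored 7, the mean of 'Yes' weeks is (4.08 − 7s)/(1 − s). For s = 0.3, 0.4 and 0.5 this is 2.83, 2.14 and 1.17. Filling with 4.08 overstates the week by 1.25, 1.94 and 2.92 days. The share s is assumed.

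**The case against.** The strongest reply is that the inference hardly changes. The test is of the arm difference. Even the largest shift found, about 2 days, compares with a 20-day planned effect and a 6.1-day standard error, and one plausible model gives almost no shift. This stands: the defect lies mainly in the reported arm means.

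Second, Step 1 improves on complete case, which section 6.8 itself says may underestimate SFDs. In the Markov model the complete-case shortfall in the control-like arm is 2.8-4.6, 6.5-11.0 and 12.1-20.3 days at 2%, 5% and 10% blanks, so Step 1 removes a little over half. With days independent within 'Yes' weeks it removes about a third (for example, from 5.8 to 3.7 days at 5%). This also stands, but the remaining bias is avoidable.

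Third, partial blanks may be rare. Protocol section 8.1 describes a Y/N prompt for each day and reminders until the survey is completed or closed, and section 10.1.9 has missing observations flagged. No document supports 5-10% blanks, although section 6.8 does expect some item non-response.

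Several stronger readings are tempting and not supported:

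- That imputed totals are biased low in every case. Only the second condition in the footnote produces this bias. Whole-day blanks unrelated to symptoms do not, and heavier skipping on symptomatic days could reduce or reverse it.
- That many caregivers will tick only 'Yes' items, so that their symptom-free days are filled as symptomatic. The protocol describes Yes/No responses and gives no such rate.
- That option 2 must ignore the weekly 'Yes'. Section 6.8 describes multiple imputation as using other observed variables, though option 2 itself names only other weeks and symptom duration.

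**Conclusion.** The point holds in conditional form. If caregivers leave some but not all daily items blank, and blanks are unrelated to the answer, the footnote makes symptom-free days more likely to be missing, and Step 1 biases imputed mean SFDs low. The direction follows from the SAP's rules under those conditions; the size rests on assumed blank rates and symptom models. Across the models, arm means are low by roughly 1-2, 2-4.5 and 4-9 days at 2%, 5% and 10% blanks, and the arm difference shifts by near 0 to about 2 days.

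Separately, Step 2 option 1 overstates a 'Yes' week with no daily entries by about 1.3-2.9 days if 30-50% of weeks are 'No'. The number of such weeks is unknown, so the two opposing errors cannot be netted into one trial-level figure.

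A reader might also infer that pooled standard errors are materially too small, because Step 1 reads as a single fill ahead of weekly multiple imputation. The wording points that way, but the effect was not quantified and no claim is made about its size.

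**What to change.** In SAP section 6.8, replace the Step 1 fill with imputation of each missing day's binary symptom-free status, done inside each multiply imputed data set so that its uncertainty is pooled. Use as predictors the items answered that day, the other days of that week and the weekly 'Yes' (in practice, fit the model to 'Yes' weeks). For a 'Yes' week with no daily entries, impute from 'Yes' weeks only, under either Step 2 option.

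Simply counting partly answered all-'No' days as symptom-free is not a substitute: in the Markov model it overshoots, by about +0.7, +1.8 and +3.7 days at 2%, 5% and 10% blanks. Nor is imputation of every item needed, which would mean 4 × 168 = 672 binary items per child.

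The cost is SAP wording and modest extra programming. No further data or participants and no EDC change are needed. The wording should be settled before treatment codes are opened.

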#### Step 2 option 1: Simple imputation at the weekly level

If the caregiver fails to submit the weekly survey (i.e., During the last full week, did your child have any coughing, wheezing, or trouble breathing?) or fails to report any symptom information for seven days of the week, simple imputation will be conducted at the weekly level. The SFDs of the missing weeks will be imputed based on the average SFDs of the observed weeks.

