The parent(s)/guardian(s) will submit a brief weekly online survey (via the EDC platform) that they receive via text or email. The alternative is a scheduled phone call with a standard script with the study coordinator or other qualified personnel from the study site research team. Parent(s)/guardian(s) of participants will receive a text or email reminder to complete the survey if it is not completed within 1 day of original due date. If a survey remains incomplete, the research team will continue to provide reminders to the parent/guardian until it is completed or closed.

The weekly survey will capture 4 elements: 1) the child's symptoms for the week, 2) number of healthcare visits, 3) time away from home, 4) study equipment use.

Each family will receive a visual tool (paper form named "Symptom Recall Tool") with the written questions as a prompt/reminder of what will be asked. The family will receive a booklet with a page of the Symptom Recall Tool for each week of the study. The Symptom Recall Tool is an aid for reporting and will not be collected. We estimate that the weekly survey will take 1-5 minutes to complete electronically.

- **Symptom survey:** The survey captures three daytime symptoms (cough, wheeze, trouble breathing) and nighttime awakenings due to cough. The responses to the symptom survey in the EDC will be used to determine SFDs. The questions have been used previously to measure SFDs after bronchiolitis over a similar time frame of approximately 6 months in a study testing whether an intervention reduces post-bronchiolitis symptomatic days.⁵

The questions are based on the Bronchiolitis Caregiver Diary, a validated measurement tool for respiratory symptoms after acute bronchiolitis.³⁷ These questions have been used to follow post-bronchiolitis symptoms over a 20-week period, similar to this study.⁵

- The survey will ask whether the child had any cough, wheeze, or trouble breathing this week (Y/N).
 - If No, they will move on to the next section for healthcare visits.
 - If Yes, they will receive a prompt for each day to respond Y/N for the presence of the symptom and if there are symptoms present, the survey will ask if any medications were used for respiratory symptoms (family to list names of medications).

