#### **Secondary endpoint 1 unscheduled healthcare visits (UHV):**

For the secondary endpoint 1 of UHV, if the missing data are caused by missed submission of the weekly survey or reporting the counts of the visits for a caregiver, the AE reports will be used as resources to calculate the number of visits during the missing weeks. The number of unscheduled healthcare visits of the missing week will not be imputed using a statistical algorithm since the imputation may overestimate the number of visits if there is no information in the AE reports about hospitalizations, ER, or other medical care visits.

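### A submitted week answered Yes but with blank or partly blank daily items can be imputed at up to seven symptom-free days, although the Yes allows at most six

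*SAP*

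**What the plan says.** **Survey.** Protocol section 8.1 opens the symptom survey with one weekly Yes/No question on cough, wheeze or trouble breathing. After a No, "If No, they will move on to the next section for healthcare visits". Only a Yes opens the day-by-day prompts. SAP section 6.6.1 scores a No week as seven symptom-free days (SFDs).

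**Step 1, daily level.** This applies to a Yes week in which the caregiver "fails to report symptoms (or no symptoms) for at least one day in seven days of the week". For such a week, "we will compute the frequency of symptom-free days using the remaining observed days of the week", and the resulting probability is used to fill the missing day.

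**Step 2 option 1, simple weekly imputation.** The trigger is either a missing survey or weekly answer, or a caregiver who "fails to report any symptom information for seven days of the week, simple imputation will be conducted at the weekly level". The fill is this: "The SFDs of the missing weeks will be imputed based on the average SFDs of the observed weeks".

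**Step 2 option 2, multiple imputation.** If the survey is not submitted or "no information was provided for seven days of the week, the SFDs of the week will be coded as missing". The stated basis for prediction is "the correlations between the missing weeks and other observed weeks", plus the duration of bronchiolitis symptoms. The process repeated at least 10 times is the weekly one.

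**Healthcare visits.** For secondary endpoint 1, "the AE reports will be used as resources to calculate the number of visits during the missing weeks". No matching rule exists for SFDs.

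**Role of imputation.** SAP section 6.6.1 makes complete case the primary analysis, and section 6.8 presents imputed results with it. Protocol section 9.4.2 says that missing primary-endpoint data in the ITT population will be imputed.

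**The concern.** A No week never needs daily entries, and a missing weekly answer has its own trigger. What remains under the no-daily-information trigger is the week in which the caregiver said Yes and left all seven days blank. The trial then knows that the child had symptoms on at least one day, yet both Step 2 options treat the week like one about which nothing is known.

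Step 1 has a related gap. It starts from the Yes but does not hold the result to it, so a Yes week can end with seven SFDs. Its fill is also described as a simple imputation outside the repeated weekly step, so its uncertainty would not be carried into the pooled standard error.

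At stake are imputed values that contradict recorded answers, arm means shifted upward, and possibly a distorted contrast. The missingness can arise only in weeks with symptoms, and the answer that explains it is not used.

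**Working it through.** **1. The plan's own figure.** Inputs from SAP section 3.4: difference 20 days, SD 43, 98 per arm; two-sided 0.05 from Protocol section 9.4.1. Effect size 20/43 = 0.465. Two-sample t-test power at 98 per arm is 0.900 (normal approximation 0.902). The figure reproduces. The standard error of the contrast is 43 × √(2/98) = 6.14 days, which is the scale for what follows.

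**2. The rules applied to single weeks.**
- *Empty Yes week, simple imputation.* Take a child with 23 observed No weeks and one Yes week with no daily entries, averaging within child. The fill is 7 and the total is 23 × 7 + 7 = 168. The Yes allows at most 23 × 7 + 6 = 167.
- *Step 1.* Take a Yes week with six observed symptom-free days and one missing day. The probability is 6/6 = 1, so the missing day is filled as symptom-free and the week scores 7. The note to SAP Figure 3 makes partial days count here: a day with three No answers and one blank is missing.

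**3. Overstatement per empty Yes week.** At the design mean an average week has 98/24 = 4.08 SFDs. Let q be the share of No weeks, which the documents do not give. The mean of Yes weeks is then (4.08 − 7q)/(1 − q).

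| q (assumed) | Mean of Yes weeks | Excess of the average-week fill |
|---|---|---|
| 0.1 | 3.76 | 0.32 |
| 0.2 | 3.35 | 0.73 |
| 0.3 | 2.83 | 1.25 |
| 0.4 | 2.14 | 1.94 |
| 0.5 | 1.17 | 2.92 |

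**4. Effect on arm means and contrast.** Simulation: daily Markov chain with beta-distributed child propensity, 40,000 children per arm, means 98 and 118 of 168 days, control SD about 43, assumed day-to-day persistence 0.70-0.92. A set share of Yes weeks lost all daily data and was filled with the child's observed-week mean.

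| Share of Yes weeks empty (assumed, equal by arm) | Control mean overstated | 20-day contrast shrinks by |
|---|---|---|
| 10% | 1.5-2.4 days | 0.1-0.4 day |
| 20% | 3.2-5.0 days | 0.3-0.8 day |

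Against the standard error, 0.4/6.14 = 6.5% and 0.8/6.14 = 13%. Power would fall from about 90% to about 89% and 87.5%. Filling from the child's other Yes weeks left an error below 0.1 day. For Step 1, with one to four days missing at random, about 1-13% of the affected Yes weeks scored 7.

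**5. Unequal frequency by arm.** One extra empty Yes week per child in one arm would move the contrast by 0.73 day (q = 0.2) to 1.94 days (q = 0.4), in a direction set by which arm has more.

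**The case against.** **The effect on the trial's question is small.** This stands. Most of the shift is common to both arms and cancels. The remainder pulls toward zero and is a small fraction of one standard error. A reader might infer that the treatment effect is materially biased; the figures do not support that at equal rates, and nothing in the documents suggests unequal ones.

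**Imputation is not the SAP's primary analysis.** This stands in part. A reader might infer that the primary result is distorted. Under the SAP the complete-case result is primary, and the SAP expects that analysis to err the other way, by undercounting SFDs. Yet the protocol calls for imputation and the SAP reports it in any case. Which document governs is a separate question.

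**The Yes is not discarded.** Correct for Step 1, which is triggered by it. The loss concerns weeks with all seven days empty. If the bare Yes were counted as symptom information, such weeks would have no rule at all, because Step 1 needs observed days.

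**Frequency and method are uncertain.** This stands. The SAP lists incomplete symptom questions as a source of missing data but gives no rate, and flagged missing entries are to be followed up. The simulation covers simple within-child imputation only, while the SAP does not say whether the average is within or across children. It also warns against simple imputation once more than 10% of participants have missing data. Multiple imputation was not simulated, and the general missing-data text allows other observed variables as predictors. SAP Figure 3, which may show the routing, is not visible in the available text.

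**A fill of exactly 7 is an edge case.** Correct: it needs every averaged week, or every observed day in Step 1, to be symptom-free. The common error is an overstated fill below 7.

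**Adverse-event reports.** A reader might infer that many weeks with a documented respiratory visit would be filled as symptom-free. Protocol section 8.3.1 limits recording to severe, serious and intervention- or equipment-related events, so few weeks qualify. A visit also does not give a count of symptomatic days. This part is unquantified.

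**Conclusion.** The point holds as a defect in the imputation rules. As written, both Step 2 options treat an empty Yes week as if nothing were known about it, and Step 1 can return seven SFDs in a week reported as symptomatic. These are stated rules that can contradict recorded answers.

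The practical weight is modest. On the assumptions above, it lies mainly in the imputed arm means, by about 1.5-5 days, and hardly in the contrast, by about 0.1-0.8 day. These sizes rest on assumed rates of 10-20% equal in both arms, assumed persistence, and within-child averaging. No size can be given for the multiple-imputation option. The case for change is that the rules conflict with data in hand and are easy to repair, not that the effect is large.

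**What to change.** Amend SAP section 6.8 as follows.

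1. **Step 2.** Separate the Yes week with no daily entries from the unsubmitted survey. Impute it within 0-6, either from Yes weeks or with the weekly answer as a predictor in the multiple imputation.
2. **Step 1.** Require at least one symptomatic day in any Yes week after filling.
3. **Uncertainty.** Repeat the Step 1 draw inside each imputed data set.
4. **Wording.** State whether the Step 2 average is within child or across children, and make Figure 3 agree with the revised text.
5. **Optional.** For unsubmitted weeks, add an indicator of an AE- or SAE-documented respiratory event to the imputation model. Expect it to inform few weeks.

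Report the number of empty Yes weeks by arm, so that readers can see whether the equal-rate assumption is reasonable. The cost is SAP wording and a few lines of code; every variable is already collected.
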